8.2 Subject Identification and Replacement of Subjects

Each subject will be assigned a unique subject identifier. This unique identifier will be on all eCRF pages.

Subjects within the initial trial subset of 18 subjects (stage 1 and 2) and in the AITL expansion cohort who do not receive at least one dose of tipifarnib will be replaced. Subjects within the initial trial subset of 18 subjects (stage 1 and 2) and in the AITL expansion cohort who are unable to provide archival tumor tissue by the end of Cycle 1 and who did not have a biopsy performed prior to initiation of tipifarnib treatment will be replaced. Replacement subjects will

have available tumor tissue identified at the time of screening. In addition, subjects with archival tissue that is of insufficient quality for biomarker evaluation, may be replaced.

8.3 Assignment to Treatment Groups

This is a nonrandomized study. Subjects will be enrolled sequentially.

8.4 Removal of Subjects from Treatment or Assessment

Subjects may withdraw their consent to participate in this study at any time without prejudice. The Investigator must withdraw from the study any subject who requests to be withdrawn. A subject's participation in the study may also be discontinued at any time at the discretion of the Investigator and in accordance with his/her clinical judgment. Every effort should be made to complete, whenever possible, the tests and evaluations listed for the End of Treatment visit. The Sponsor must be notified of all subject withdrawals as soon as possible. The Sponsor also reserves the right to discontinue the study at any time for either clinical research or administrative reasons and to discontinue participation by an individual Investigator or site for poor enrollment or noncompliance.

Overall, the reasons for which the Investigator or Kura Oncology may withdraw a subject from study treatment include, but are not limited to, the following:

- Subject experiences disease progression
- Subject experiences unacceptable toxicity
- Subject requires more than 2 dose reductions
- Subject experiences toxicity that is deemed by the Investigator to be no longer safe for the subject to continue therapy
- Subject requests to withdraw from the study treatment
- Subject requires or has taken medication prohibited by the protocol
- Subject is unwilling or unable to comply with the study requirements
- Subject withdraws consent to collect health information
- Subject was erroneously admitted into the study or does not meet entry criteria
- Subject is lost to follow-up
- Subject becomes pregnant

Subjects will return for an End of Treatment visit within approximately 30 days after the last administration of the study drug (or sooner if another anticancer therapy is to be initiated). If a subject fails to return for scheduled visits, a documented effort must be made to determine the reason. If the subject cannot be reached by telephone after 2 attempts, a certified letter should be

sent to the subject (or the subject's legally authorized representative, if appropriate) requesting contact with the Investigator. This information should be recorded in the study records.

Prior to enrollment into the study, the Investigator or designee must explain to each subject, that the subject's protected health information obtained during the study may be shared with the study Sponsor, regulatory agencies, and IRB/IEC in order to analyse and evaluate study results. It is the Investigator's (or designee's) responsibility to obtain written permission to use protected health information per country-specific regulations, such as HIPAA in the US, from each subject, or if appropriate, the subject's legally authorized representative. If permission to use protected health information is withdrawn, it is the Investigator's responsibility to obtain a written request from the subject, to ensure that no further data will be collected from the subject and the subject will be removed from the study.

8.5 Premature Discontinuation of the Trial

This trial may be discontinued prematurely in the event of any of the following:

- New information leading to a judgment of unfavorable risk-benefit of tipifarnib becomes available, e.g. due to: Evidence of inefficacy of tipifarnib in PTCL, occurrence of significant previously unknown adverse reactions or unexpectedly high intensity or incidence of previously known adverse reactions, or other unfavorable safety findings in the PTCL patient population. Evidence of inefficacy may arise from this trial or from other trials; unfavorable safety findings may arise from clinical or non-clinical examinations, e.g. toxicology.
- Sponsor's decision that continuation of the trial is unjustifiable for medical or ethical reasons.
- Poor enrollment of subjects making completion of the trial within an acceptable time frame unlikely.
- Discontinuation of development of tipifarnib by the Sponsor.
- Request by a Health Authority.

Health Authorities and IRBs/IECs will be informed about the discontinuation of the trial in accordance with applicable regulations. In the case of premature discontinuation of the study, the investigations scheduled for the End of Treatment assessment should be performed and the appropriate eCRF section completed.

8.6 Definition of End of Study

For administrative and safety reporting purposes, the end of this clinical study is defined as 12 months from enrollment of the last enrolled study subject. If the last enrolled study subject discontinues treatment within 12 months of study enrollment, the End of Study will occur no earlier than the date of the last enrolled subject's safety follow-up assessment performed

approximately 30 days after treatment discontinuation (or until initiation of another anti-cancer therapy). At the time of End of Study, provisions will be made to transition all remaining study subjects who demonstrate sustained clinical benefit beyond the end of the study to other means of continued treatment with appropriate safety monitoring, e.g. single patient treatment protocol.

9 TREATMENTS

Subjects will receive tipifarnib as monotherapy in this study. In the absence of unacceptable tipifarnib related emergent toxicity or disease progression, subjects may receive treatment with tipifarnib for up to 12 months at the discretion of the Investigator. Treatment beyond 12 months may continue upon agreement of the Investigator and the Sponsor. Kura Oncology, Inc or its designee will provide the study site with a supply of tipifarnib sufficient for the completion of the study.

All study subjects will be also eligible to receive best supportive care (BSC) defined as any standard supportive measures that are not considered a primary treatment of the disease under study, including the use of growth factors (i.e. GCSF) for myelosuppression. BSC will be provided by the study sites.

9.1 Investigational Product (IP)

Tipifarnib is a small molecule being developed as a potent, selective inhibitor of FTase for the treatment of cancer and other malignancies.

9.1.1 Product Characteristics

Tipifarnib film-coated tablets for oral administration are supplied in HDPE bottles. Two strengths (100 mg and 300 mg) of tablets are provided containing either 100 or 300 mg of tipifarnib active substance, respectively. In addition to the active substance, the tablets contain the following inactive ingredients: lactose monohydrate, maize starch, hypromellose, microcrystalline cellulose, crospovidone, colloidal anhydrous silica, and magnesium stearate. The nonfunctional, taste-masking film coatings contain hypromellose, titanium dioxide, lactose monohydrate, polyethylene glycol, and triacetin. Each strength of tablet has the same excipients but the quantitative composition is slightly different. Further information can be obtained from the current version of the Investigator's Brochure.

9.1.2 Storage and Labeling

At a minimum, the label of each bottle of tipifarnib tablets shipped to the study sites will provide the following information: batch number/lot number, study identification, required storage conditions, directions for use, and country specific required caution statements (including "New Drug – Limited by United States federal law to investigational use" language).

Tipifarnib accountability records will be maintained by the pharmacy or designated drug preparation area at the study sites. Upon receipt of tipifarnib supplies, the pharmacist or designated study site investigational drug handler will inventory tipifarnib (separately for each strength, if applicable) and complete the designated section of the shipping form. The shipping/inventory form must be sent to Kura Oncology, Inc or its designee, as instructed.

Tipifarnib should be stored at controlled room temperature 15 to 30 C (59 to 86 F). All study supplies must be kept in a restricted access area.

9.2 Treatment Administration

Tipifarnib will be administered with food at a starting dose of 300 mg, orally, bid on days 1 - 21 of 28 day treatment cycles. Subjects who received tipifarnib bid on Days 1 – 7 and Days 15 – 21 during the conduct of earlier versions of this protocol may remain on that dose regimen at the discretion of the investigator. Alternatively, the subject may transition to receive a dose of 300 mg, orally with food, bid on days 1-21 of 28 day treatment cycles beginning on Day 1 of their next cycle.

The first study dosing (Cycle 1 Day 1) will take place in the study clinic. Tipifarnib will be administered orally with a meal in the morning and again approximately 12 hours later at approximately the same times each treatment day. Tablets should be swallowed whole with water (~8 oz. or 250 mL), but may be chewed or crushed if the Investigator deems it necessary. Use of percutaneous endoscopic gastrostomy tubes is allowed at the judgment of the Investigator. If a dose is vomited or partially vomited, it should not be replaced with a new dose.

Subjects may use proton pump inhibitors or H2 antagonists during the treatment portion of this study. However, subjects should be instructed to use antacids (magnesium or aluminum containing products) at least 2 hours before or after intake of oral study drug.

Subjects will be provided with diaries with instructions to record the date and time of each dose and asked to bring the diaries and tablet bottles to each clinic visit for subject compliance and drug accountability review by the site staff.

9.3 Treatment Assignment

Treatment will be conducted in an open label manner. Kura Oncology, Inc or its designee will assign a subject number identifier for each subject that is enrolled into the study. Study sites cannot enroll or start dosing the subject without receiving the assigned subject number.

9.4 Dose Selection

In the majority of its phase 2 program, tipifarnib was given orally at a dose of 300 mg bid for 21 days, followed by 1 week of rest, in 28 day treatment cycles (3 weeks on/1 week off schedule). Prior studies have shown that [REDACTED]

[REDACTED] those shown to demonstrate anti-tumor activity in preclinical tumor models. In the AML

studies which administered tipifarnib at doses up to 600 mg bid for 21 days in 28-day treatment cycles, the most common adverse events were myelosuppression, gastrointestinal disorders, fever, fatigue, hypokalemia, rash, renal impairment, and dyspnea. The most common drug-related grade 3 or 4 events were myelosuppression, hypokalemia, fatigue, and rash. Thrombocytopenia, renal impairment, rash, and sepsis were the most common adverse events that led to discontinuation. In the completed MDS study (INT-28) which administered tipifarnib at a dose of 300 mg bid for 21 days in 28-day treatment cycles, the most common adverse events were myelosuppression, fatigue, diarrhea, nausea, and rash. The most common drug-related grade 3 or 4 events were myelosuppression, fever, pneumonia, bacterial infection, and rash. The most common adverse events that lead to discontinuation were thrombocytopenia and rash.

No data are currently available in the sponsor's database on the safety and tolerability of tipifarnib from prior studies in subjects with lymphoma. However, a phase 2 investigator-initiated study of tipifarnib was conducted in 93 adult patients with relapsed or refractory lymphoma. Patients received tipifarnib 300 mg twice daily on days 1-21 of each 28-day cycle. The median number of prior therapies was 5 (range, 1-17). For the aggressive B-cell, indolent B-cell, and T-cell and Hodgkin lymphoma (HL/T) groups, the response rates were 17% (7/42), 7% (1/15), and 31% (11/36), respectively. Of the 19 responders, 7 were diffuse large B-cell non-Hodgkin lymphoma (NHL), 7 T-cell NHL, 1 follicular grade 2, and 4 HL. The median response duration for the 19 responders was 7.2 months (mean, 15.8 months; range, 1.8-62). The grade 3/4 toxicities observed were fatigue and reversible myelosuppression ([Witzig 2011](#)).

In the original version and amendments 1 – 4 of the current study, an effort was made to evaluate the safety and tolerability of administering tipifarnib [REDACTED]

[REDACTED] two trials in MDS and AML subjects investigating alternate week dosing, i.e. 7-day bid dosing followed by 7 days of rest ([Kurzrock 2008](#), [Kirschbaum 2011](#)).

Based on these data, a [REDACTED] for evaluation in this study. However, [REDACTED]

[figure not shown]
[REDACTED] in amendment 3. Ongoing review of preliminary data from subjects enrolled in stages 1 and 2 of the current study suggested that toxicities were consistent with known safety profile of tipifarnib. No subject discontinued due to AEs. Grade ≥ 3 TEAEs occurring in $> 10\%$ of subjects were hematology-related and included neutropenia (83%), thrombocytopenia (61%), leukopenia (50%), anemia (39%), febrile neutropenia (33%) and lymphopenia (17%). Myelosuppression was manageable with treatment interruption, dose reductions and/or growth factor support.

[figure not shown]
As of July 2017, four subjects required further dose [REDACTED] in alternating weeks, including the two ongoing subjects enrolled in stages 1 and 2 of the study. [REDACTED] [REDACTED] over a 28-day treatment cycle achieved with the prior regimen (300 mg bid on days 1 – 21 of 28-day treatment cycles).

[figure not shown]
Based on these preliminary data, it was concluded that the [REDACTED] over a 28-day cycle.

[figure not shown]
Therefore, in Amendment 5 the dose and dose regimen was revised to tipifarnib 300 mg bid for 21 days in 28-day treatment cycles. This dose and dose regimen is expected to be well tolerated and to provide potential clinical benefit to subjects with PTCL. In addition, the current study allows for step-wise 100 mg dose de-escalation based on subject tolerability. Subjects who received tipifarnib [REDACTED] during the conduct of earlier versions of this protocol may remain on that dose regimen at the discretion of the investigator. Alternatively, the subject may transition to receive a dose of 300 mg, orally with food, bid on days 1-21 of 28 day treatment cycles beginning on Day 1 of their next cycle.

The data obtained from this study will be used to select the optimal dose and dose regimen to support the further development of tipifarnib in subjects with PTCL.

9.6 Treatment of Overdose

An overdose is defined as any dose greater than 20% over the scheduled daily tipifarnib dose. Any overdose must be recorded in the trial medication section of the eCRF. There is no known antidote for tipifarnib. In the event of overdose of tipifarnib, subjects should receive appropriate advice and supportive medical care by the investigator or his/her designee and be followed-up accordingly.

For monitoring purposes, any case of overdose – whether or not associated with an AE (serious or non-serious) – must be reported to the Sponsor in an expedited manner.

9.7 Blinding

This is an open label study with no placebo or comparators.

9.8 Treatment Compliance

The importance of treatment compliance should be emphasized to the subject. Subjects will be given study drug, dose diaries and detailed instructions on how to take medications at home. Subjects will be instructed to return all used and unused study drug containers at each study visit, unless otherwise specified per site SOP. Subject compliance with the dosing schedule will be assessed by reconciliation of the used and unused study drug at each clinic visit and review of the dosing diaries. The quantity dispensed, returned, used, lost, etc. must be recorded on the dispensing log provided.

Compliance will be monitored and documented by site personnel on the appropriate form. The site personnel will question the subject regarding adherence to the dosing schedule by reviewing the dosing diaries, recording the number of tablets (and strengths, if applicable) returned, the date returned, and determining treatment compliance before dispensing new medication to the study subject.

9.9 Investigational Product Accountability

The Investigator or designee is responsible for maintaining accurate records (including dates and quantities) of IP received, subjects to whom IP is dispensed (subject by subject specific accounting), and IP lost or accidentally or deliberately destroyed. The Investigator or designee must retain all unused or expired study supplies until the Sponsor's designated trial monitor has confirmed the accountability data or a waiver for site drug destruction prior to monitoring visits is provided by the Sponsor.

9.10 Return and Disposition of Clinical Supplies

Unused study drug must be kept in a secure location for accountability and reconciliation by the Sponsor's designated clinical trial monitor. The Investigator or designee must provide an explanation for any destroyed or missing study drug or study materials.

Study drug may be destroyed on site, per the site's standard operating procedures, but only after the Sponsor or its designee has granted approval for drug destruction. All study drug destroyed on site must be documented.

Documentation must be provided to the Sponsor or its designee and retained in the Investigator's study files. If a site is unable to destroy study drug appropriately, the site can return unused study drug to the Sponsor or its designee upon request. The return of study drug or study drug materials must be accounted for on a form provided by the Sponsor or its designee.

All study drug and related materials should be stored, inventoried, reconciled, and destroyed or returned according to applicable state and federal regulations and study procedures.

9.11 Prior and Concomitant Medications

All prescription and over-the-counter medications taken by a subject within 28 days before the first study drug administration will be recorded in the eCRF.

Supportive care medications considered necessary for the subject's safety and well-being may be given at the discretion of the Investigator. Any concomitant medications added or discontinued during the study should be recorded on the eCRF.

BSC will be provided by the clinical study sites according to local guidelines and standard practices.

Furthermore, the following treatments are allowed during the trial:

- IV hydration
- Correction of electrolyte deficiency.
- Hematopoietic growth factors and transfusions of blood or blood products in subjects who are experiencing hematological toxicity in accordance with standard institutional practice.

[figure not shown]
- Radiotherapy for pain control against non-target lesions as long as it does not influence bone marrow function.
- Total tumor resection in responding subjects who have become candidates for curative resection.

Any additional concomitant therapy that becomes necessary during the trial and any change to concomitant drugs must be recorded in the corresponding section of the eCRF, noting the name, dose, duration and indication of each drug.

9.12 Non-permitted Treatments

Use of the following medications and therapies is not allowed during the trial:

- Investigational agents other than tipifarnib.
- Any other anticancer therapy, including radiation or surgery, for the primary disease under study with the exceptions of palliative treatment.
- Subjects should not use enzyme-inducing anti-convulsants (e.g. phenytoin, phenobarbital, and carbamazepine) while taking tipifarnib. If needed, subjects may use non-enzyme-inducing anti-convulsants (e.g. gabapentin, topiramate, valproate) while taking tipifarnib.
- High dose systemic corticosteroids or any other immunosuppressive drugs except glucocorticosteroid treatment administered with a daily dose of $\leq 20\text{mg}$ prednisone or equivalent, and single doses for the management of treatment-related adverse events or for premedication of BSC agents.

If the administration of a non-permitted concomitant drug becomes necessary during the trial, e.g., because of AEs or disease progression, the subject in question will be withdrawn from the trial, and the subject's data which will have been obtained before the withdrawal may be used for safety and efficacy evaluations.

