10.1 Efficacy Variables

Radiological and/or physical assessments of the tumor lesions will be made at screening (4 weeks before the first study drug administration) and at regular intervals as indicated in the schedule of activities (Table 1). Additional tumor assessments may be conducted at the judgment of the investigator. The imaging schedule (approximately every 8 weeks during the subject's first 6 months on study, thereafter every 12 weeks) should be maintained regardless of dosing delays or additional imaging assessments performed. Subjects who discontinue treatment for reasons other than disease progression must continue tumor assessments until disease progression, withdrawal of their consent to study procedures or initiation of another anticancer therapy. Efficacy assessments may also be conducted at treatment discontinuation (End of Treatment visit) if the reason for the treatment termination is other than disease progression and a tumor assessment was not done within 8 weeks before treatment discontinuation (assessment must be conducted before additional anti-tumor therapy is started). Scans at the End of Treatment visit will be also conducted if required to confirm response to treatment.

Lesions to be included in the tumor assessments should follow the Lugano Classification criteria and/or mSWAT. In subjects with FDG avid lymphomas, PET-CT is the preferred scanning method for screening and all subsequent tumor assessments (Cycle 2, Cycle 4, Cycle 6, etc.). In subjects with low or variable FDG avid lymphomas, Spiral CT with contrast is the preferred scanning method for screening and all subsequent tumor assessments (Cycle 2, Cycle 4, Cycle 6, etc.). Subjects with contrast allergy may use non-contrast CT or MRI, whichever is required to adequately assess all disease. The same method of imaging must be used throughout a subject's participation on this study.

Bone marrow assessment (biopsy or PET assessment) will be performed at screening within 28 days of Cycle 1 day 1. If baseline bone marrow assessment was positive for lymphoma, a bone marrow biopsy or PET evaluation would be mandatory to confirm a complete response (i.e. after radiographic assessment).

Objective response (complete response and partial response) as determined by the subject's best tumor response, duration of response, and time to progression will be assessed using the Lugano Classification and/or mSWAT.

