11.7.1 Follow Up after Disease Progression

Upon disease progression, all subjects will be followed approximately every 12 weeks for survival and the use of subsequent therapy until either death or 12 months after accrual of the last study subject, whichever occurs first. Information on survival and subsequent anticancer therapy may be collected by phone.

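### Protocol 9.12 removes from the trial a subject who needs a prohibited drug, while 8.4, 8.1, 10.1, 11.7 and 11.7.1 keep such a subject in follow-up; PFS and DOR could be informatively censored

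*Protocol*

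**What the plan says.** Four sets of passages bear on this.

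- **Protocol 9.12.** The trigger is "If the administration of a non-permitted concomitant drug becomes necessary during the trial, e.g., because of AEs or disease progression". The consequence is that "the subject in question will be withdrawn from the trial". Of the subject's data, only those from before that date are mentioned: "data which will have been obtained before the withdrawal may be used for safety and efficacy evaluations".
- **Protocol 8.4.** The investigator or sponsor "may withdraw a subject from study treatment include, but are not limited to, the following"; one listed reason is "Subject requires or has taken medication prohibited by the protocol".
- **Follow-up rules.** Protocol 10.1 states: "Subjects who discontinue treatment for reasons other than disease progression must continue tumor assessments until disease progression", with consent withdrawal and another anticancer therapy as the other end points. Section 8.1 says the same. Table 1 footnote 8 omits the new-therapy stop, and 11.7 names progression only. Section 11.7.1 adds: "Upon disease progression, all subjects will be followed approximately every 12 weeks for survival and the use of subsequent therapy".
- **Analysis rules.** Protocol 12.2.1 wants PFS to take account of scans made after treatment stops. SAP 6.4 treats dropouts without an event as censored. SAP 8.2 censors PFS at the last evaluable assessment when a subject goes off study without documented progression. No SAP rule addresses a withdrawal under 9.12, and the OS censoring list in SAP 8.3 does not name it.

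On local treatment, 9.12 bars surgery and radiation for the primary disease except as palliation. Section 9.11 allows "Total tumor resection in responding subjects who have become candidates for curative resection", and 11.7 permits irradiation of residual tumour in responders.

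**The concern.** The same event carries two consequences: mandatory removal from the trial in 9.12, and optional removal from treatment in 8.4. A site cannot follow 9.12 literally and also carry out the scans and survival contacts that the other sections require.

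The analysis is exposed because 9.12 gives adverse events and disease progression as its own examples. Subjects who leave for those reasons may be doing worse than those who stay. Kaplan-Meier estimation assumes that censored subjects have the same outlook as those still at risk. If subjects close to progression are censored, the PFS and DOR curves sit too high. Making the use of earlier data optional adds a second weakness in an open-label trial with investigator-assessed response, because whether those data count is left to choice.

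**Working it through.** **1. Same event, side by side**

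| Point | 9.12 | Other sections |
|---|---|---|
| Force | Mandatory | Optional (8.4) |
| What ends | The trial | Study treatment (8.4) |
| Scans after stopping without progression | None mentioned | Required (8.1, 10.1, 11.7) |
| Survival contact after progression | None mentioned | All subjects (8.1, 10.1, 11.7.1) |

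Loose wording is not a safe explanation. Section 8.4 itself speaks separately of leaving the study on request and of being taken off treatment.

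**2. Which triggers reach which endpoint**

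- *Documented progression, then a prohibited drug.* The PFS or DOR event is already counted. Only survival and later-therapy data can be lost.
- *Another anticancer therapy before progression.* Sections 8.1 and 10.1 already end scans there, and 12.2.1 already censors DOR. Section 9.12 adds little for tumour follow-up.
- *A prohibited non-anticancer drug before progression.* The 9.12 list gives enzyme-inducing anticonvulsants, high-dose systemic corticosteroids and other immunosuppressants. Here 9.12 ends scans that 8.1, 10.1 and 11.7 require. This is where PFS and DOR are exposed.

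**3. Illustrative size**

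The plan gives no figure to reproduce. Inputs:

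- True median PFS of 134 days, from Protocol 5.2 (8 early subjects of this trial with reference 3'UTR).
- Exponential PFS (assumption).
- Scans every 56 days, as in the protocol's 8-weekly schedule, here kept throughout.
- Share f withdrawn (assumption). Each withdrawn subject is censored at the last scan before progression; every other progression is dated at its exact time.

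Rate: λ = ln 2 / 134 = 0.005173 per day. Chance of progressing within one 56-day interval: q = 1 − exp(−0.005173 × 56) = 0.2515.

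Of those at risk at the start of an interval, fq are censored there and (1 − f)q have events. The Kaplan-Meier factor per interval is therefore 1 − (1 − f)q/(1 − fq) = (1 − q)/(1 − fq).

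For f = 0.10 the factor is 0.7485/0.97485 = 0.7678. After two intervals (112 days) the curve is at 0.5895; a third would take it to 0.4527. Within the third interval, solve 1 − 0.9(1 − e^(−λu))/0.97485 = 0.5/0.5895. This gives u = 34.7, so the median is 112 + 34.7 = 146.7 days.

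If subjects instead leave immediately before progression, the median is 134/(1 − f).

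| Share withdrawn | Censored at last scan | Censored just before progression | Withdrawal unrelated to prognosis |
|---|---|---|---|
| 5% | 140 | 141 | 134 |
| 10% | 147 | 149 | 134 |
| 20% | 163 | 167 | 134 |

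Simulation with 400,000 subjects per setting agrees: 140.0, 146.9 and 162.6 days in the last-scan column, and about 134 in the final column.

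**4. Two limits on those figures**

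*Dating of progression.* Protocol 12.2.1 runs PFS to the first observation of progression, so medians fall on scan days. Day 22 of Cycles 2, 4, 6 and 9 is day 50, 106, 162 and 246. With the same factor and these spacings, the curve at day 162 is 0.433, 0.449, 0.466, 0.484 and 0.503 for 0%, 5%, 10%, 15% and 20% withdrawn. The observed median would stay at day 162 up to 15% and move to day 246 at 20%. The curve rises smoothly, but the median moves in a step.

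*Sampling error.* With the 65 evaluable subjects assumed in SAP 4, the standard error of an exponential median estimated by Kaplan-Meier, uncensored, is about 1/(λ√65) = 193.3/8.06 = 24 days. The last-scan shifts are 6, 13 and 29 days.

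**The case against.** The strongest reply is that little is exposed. Most triggers leave PFS and DOR untouched, as step 2 shows. Section 9.12 exempts low daily corticosteroid doses and single doses for treatment-related events. The primary endpoint is ORR, PFS and DOR are summarised descriptively, and OS is exploratory. SAP 8.2 allows sensitivity analyses on censoring and counts deaths within 126 days of the last treatment or assessment. Nothing suggests that prohibited non-anticancer drugs will be common.

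Most of this stands. It narrows the affected group and lowers the stakes, but it does not reconcile the passages. The 126-day rule helps only if the death becomes known, and the sensitivity analyses are optional and cannot recover scans that were never made.

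A reader might also infer three stronger things that the documents do not support:

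- *That responders who have curative resection or irradiation of residual tumour must be withdrawn.* The withdrawal sentence concerns a drug, while 9.11 and 11.7 expressly allow those procedures. The wording on local treatment needs reconciling, but as a separate matter.
- *That PFS and DOR will be biased.* This depends on how many subjects are withdrawn and how closely withdrawal tracks prognosis, and neither is given.
- *That the primary ORR result is at risk.* The point is not made for ORR.

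**Conclusion.** The contradiction is real. It lies in current protocol text, and neither redaction nor an amendment log explains it. Followed literally, 9.12 could informatively censor PFS and DOR, mainly for subjects given a prohibited non-anticancer drug before documented progression. It could also lose survival data for subjects withdrawn at progression.

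The size is unknown. The upward shift of 6 to 29 days in a 134-day median is near the worst case. It assumes that 5% to 20% are withdrawn, that every one of them was about to progress, that PFS is exponential and that progression is dated exactly. With no link to prognosis the shift is nil. This is a wording defect worth correcting because it touches the secondary endpoints and costs little to repair.

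**What to change.** 1. Reconcile 8.4 and 9.12 with 8.1, 10.1, 11.7 and 11.7.1, so that 9.12 separates stopping study treatment from leaving follow-up. Which treatment rule applies is for the sponsor to settle.
2. State in 9.12 that tumour assessments continue under the stopping rules already in 8.1 and 10.1: progression, consent withdrawal or initiation of another anticancer therapy. State that survival follow-up continues unless consent is withdrawn.
3. Align Table 1 footnote 8 and 11.7 with those stopping rules.
4. In 9.12, replace *may be used* with *will be used* for data obtained before withdrawal.
5. Add to the SAP the PFS, DOR and OS censoring rule for subjects who meet the 9.12 trigger.
6. Separately, reconcile the wording of 9.11, 9.12 and 11.7 on surgery and radiation.

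The cost is a protocol clarification and a short SAP addition. The scans and contacts are already required elsewhere in the protocol.
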